## SUMMARY

**Importance:** After a primary total knee arthroplasty (TKA), we anticipate that obese individuals are more likely to experience a of periprosthetic joint infection (PJI). Knowing the microbial profile in obese patients can potentially help in choosing the proper prophylactic measures for this group as well as tailoring the empirical antibiotics in relation to PJI in obese patients.

**Objective:** To compare incidence of PJI revisions within 2 years after TKA in obese vs non-obese OA patients. Secondarily: To compare microbial profiles of infections in these groups in two time windows: early ( $\leq 90$  days) vs late (91–730 days) and incidence of revisions due to all causes within 2 years. **Design and Setting:** We will include patients having primary knee arthroplasty using Danish national registers. Patients will be stratified into anthropometric groups, referred to as exposed and unexposed to obesity, based on their baseline Body Mass Index (BMI). Participants included in the analysis population will be followed up for 2 years, until first revision, death or migration whichever comes first.

**Participants:** We will include adult patients with available weight and height data with primary/idiopathic or secondary (due to meniscus or cruciate ligament lesion) OA who received primary TKA in the period from 2011-01-01 and 2021-02-28. Patients will be identified from the Danish knee arthroplasty register.

**Exposure and Comparator:** The cohort will be divided into obese (exposed), defined as body mass index (BMI)  $\geq 30$  kg/m $^2$ ; and non-obese (unexposed), defined as BMI  $< 30$  kg/m $^2$ .

**Main Outcomes and Measures:** The primary outcome will be revision due to prosthetic joint infection (PJI) within 730 days following TKA. Secondary endpoints will then be to examine revision due to all causes within 730 days following TKA and type of microbial infection between obese and non-obese in the first 90 days and the period from 91 days to 730 days following TKA.

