## Setting

All Danish residents have a personal identification number consistent throughout all registers making register-linkage possible. We will include patients with PJI diagnosis after their primary hip or knee

arthroplasty using Danish national registers. Patients will be followed up for 2 years, until first revision, death or migration whichever comes first.

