## Statistical Methods

We will use descriptive statistics to summarize baseline characteristics of the two groups and will compare them using standardized differences. The 2-year (730 days) cumulative incidence of PJI will be reported for both groups. Hazard ratios with corresponding two-sided 95% confidence intervals (CIs) will be estimated using a Cox proportional hazards regression model. We will fit both unadjusted (crude) models and propensity adjusted models using inverse probability of treatment weighting (IPTW). For the adjusted model, propensity scores will be calculated based on age in years, female sex, completed education, household income, comedications, and ECM (all collected prior to surgery). Subsequent stratified analyses will categorize the observed PJI cases by bacterial infection type (within the first 90 days postoperatively or between 91 days and 2 years) and compare crude proportions between groups based on the absolute risk difference with 95% confidence intervals.

[figure not shown]
We present several analyses corresponding to the main results with 95% confidence intervals rather than P values, and comply with 2 Acta Orthopaedica principles for concluding whether scientifically important differences exist:

- A statistically non-significant test is not sufficient to claim "no difference." To show "no difference," a smallest clinically relevant size of the difference (it might be 0) must be defined. If all clinically relevant differences are excluded from the difference's confidence interval, a "no difference" or similarity/comparability conclusion is reasonable.
- A statistically significant test does not necessarily imply a clinically important difference. The importance of the tested null hypothesis depends on the smallest clinically relevant difference that should be defined a priori. If the difference's confidence interval excludes all clinically irrelevant differences, a conclusion concerning the existence of a clinically important difference is reasonable.

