To evaluate imprecision in the estimated treatment effect, a clinically important difference must first be defined. Based on an expected 2-year incidence of PJI of about 1%, a 50% increase in risk would be considered clinically relevant. In a time-to-event analysis, this corresponds to a hazard ratio of 1.5. Accordingly, non-inferiority—or absence of a clinically meaningful increase in risk—will be established if the upper bound of the 95% confidence interval for the hazard ratio remains below 1.5. We will visualize the 2-year cumulative incidence of all outcomes for both groups using the cumulative incidence functions (CIFs).

**Handling of missing data and sensitivity analyses:** Missing data is unavoidable in epidemiological and clinical research and must be explained otherwise it could undermine the credibility and validity of the research results. Missing values, for either predictors or outcomes, occur in all types of medical research. Unless prompted to do otherwise, most statistical packages explicitly exclude individuals with any missing value on any of the data analyzed. The resulting so-called "available case" or "complete case" analysis is the most common "default approach" to handle missing data, although it is rarely justified. Subjects with missing weight or height will be excluded from the analysis. Missingness of data on some of the covariates used for adjusting will be ignored but the subjects will not be excluded. Patients who will be lost during the follow up period (e.g., due to death or migration) are expected to be extremely few and no systematic difference is expected to be seen.

Therefore, this missingness of outcome data will be assumed "Missing completely at random" (MCAR), as there is no evidence to suggest systematic differences between the missing values and the observed values and will be ignored. For the purpose of sensitivity, we will potentially re-do the main analysis where missing outcome data is replaced twice, using best-case imputation ( $y=0$ ; no PJI) and worst-case imputation ( $y=1$ , PJI yes).

[figure not shown]
**Figure 1 (Mockup):** study flow chart

**Table 1 (Mockup).** Baseline characteristics at time of total knee arthroplasty

|  | Obese | Non-Obese | Std. Diff |
|--|-------|-----------|-----------|
| Age, years                                 |       |           |           |
| Female Sex, no. (%)                        |       |           |           |

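### The optional imputation rerun would count recorded deaths as PJI, and giving both BMI groups the same imputed value does not yield a worst case for the hazard ratio

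*Combined protocol and SAP*

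**What the plan says.** The passage is the paragraph on missing data and sensitivity analyses within Statistical Methods. It expects little loss: "Patients who will be lost during the follow up period (e.g., due to death or migration) are expected to be extremely few". It gives no rate. It then labels this loss as missing outcome data, assumes it is missing completely at random because "there is no evidence to suggest systematic differences between the missing values and the observed values and will be ignored", and adds a check: "For the purpose of sensitivity, we will potentially re-do the main analysis where missing outcome data is replaced twice". The two values are y=0 and y=1: "replaced twice, using best-case imputation ( $y=0$ ; no PJI) and worst-case imputation ( $y=1$ , PJI yes"). Deaths are not exempted, and the imputed value does not differ by BMI group.

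Elsewhere, death is an end of follow-up. The Summary says: "Participants included in the analysis population will be followed up for 2 years, until first revision, death or migration whichever comes first". Setting has the same rule ("Patients will be followed up for 2 years, until first revision, death or migration whichever comes first"), as does Study population. Data sources lists vital and migrant status among the contents of the civil register. Statistical Methods also plans an incidence figure by group ("The 2-year (730 days) cumulative incidence of PJI will be reported for both groups") and plots ("We will visualize the 2-year cumulative incidence of all outcomes for both groups using the cumulative incidence functions (CIFs"), but does not name death as a competing event.

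**The concern.** Two things look wrong.

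First, a patient who dies without a PJI revision does not have an unknown outcome. The death and its date are in the register, and PJI revision can no longer occur. Coding that patient as a PJI case replaces the endpoint with a composite of PJI, death and migration. The y=0 run does not raise this problem, since it agrees with death precluding PJI.

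Second, what is rerun is the main analysis, which is a hazard ratio between groups. Setting every lost patient to 0, and then every lost patient to 1, gives the lowest and highest incidence within each group. The extremes of a ratio come from opposite values in the two groups. The y=0 run nearly repeats the censored analysis, and the y=1 run pulls the HR toward the ratio of the loss hazards.

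At stake is the plan's only check on loss to follow-up. If loss is similar in the two groups, the run labelled worst case would look more reassuring than the main result.

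**Working it through.** **Inputs from the plan** (Statistical Methods): 2-year PJI risk of about 1%; a 50% increase counts as relevant, so 1.5%; margin HR 1.5, judged on the upper limit of a two-sided 95% interval.

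**Assumed, not in the documents:** 40,000 patients, 40% obese (16,000 and 24,000), and all loss rates. Subscript 1 is obese and 0 is non-obese; q is the proportion lost before a PJI revision.

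**Plan's own figure.** ln(1 − 0.015) / ln(1 − 0.010) = 1.504, which agrees with the stated 1.5.

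**Without imputation.** Events are 16,000 × 0.015 = 240 and 24,000 × 0.010 = 240. SE(log HR) = √(1/240 + 1/240) = 0.0913. Upper limit = 1.504 × exp(1.96 × 0.0913) = 1.80.

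**The y=1 run.** HR = ln(1 − p1 − q1) / ln(1 − p0 − q0), with events n × (p + q). For example, at 0.5% loss in both groups, HR = ln(0.980) / ln(0.985) = 1.34. Events are 320 and 360, SE is 0.0768, and the upper limit is 1.55.

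| Equal loss | y=1 HR | Upper limit |
|---|---|---|
| 0.1% | 1.46 | 1.73 |
| 0.5% | 1.34 | 1.55 |
| 1% | 1.25 | 1.43 |

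The upper limit falls below 1.5 only above about 0.69% loss. That threshold ranges from 0.54% (60,000 patients, 50% obese) to 1.14% (20,000 patients, 30% obese).

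**Other true HRs, 0.5% equal loss.** With p1 = 1 − 0.99^HR, 0.8 becomes 0.87, 1.0 stays 1.00, 1.2 becomes 1.13 and 2.0 becomes 1.67. Equal loss pulls the estimate toward 1 from either side.

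**Unequal loss (obese / non-obese), true HR 1.50.** 0.15% / 0.1% gives 1.50; 0.2% / 0.1% gives 1.55; 0.1% / 0.2% gives 1.34; 4% / 2% gives 1.86. The loss ratio at which the y=1 HR equals the main HR is 1.49 to 1.50 for non-obese loss of 0.1% to 2%. Below that ratio the HR falls, and above it the HR rises.

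**Common against opposed values, same patients and same rate m in both groups.** The opposed runs are ln(1 − p1) / ln(1 − p0 − m) and ln(1 − p1 − m) / ln(1 − p0).

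| m | Common value (y=1, y=0) | Opposed values |
|---|---|---|
| 0.1% | 1.46 to 1.50 | 1.37 to 1.60 |
| 0.25% | 1.40 to 1.50 | 1.20 to 1.76 |
| 0.5% | 1.34 to 1.50 | 1.00 to 2.01 |

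**Cross-checks.** A separate person-time calculation, treating deaths as the only loss, gives y=1 HRs of 1.33 and 1.25 at 0.5% and 1%, and opposed values of 1.00 to 2.00 at 0.5%. In 300 simulated cohorts per scenario fitted by Cox regression, the y=0 HR (patients kept at risk to day 730) and the censored HR differed on average by 0.0002 to 0.0007 at equal loss of 0.1% to 1%, and by 0.008 to 0.016 at 3% / 2% and 4% / 2%. All figures are for the crude model; intervals under the planned weighting were not computed.

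**The case against.** The strongest reply is that no planned conclusion depends on this run. It is optional, has no mock table and feeds no decision rule. The follow-up rule already censors at death in the Cox model, so calling death missing at random changes nothing there. This stands, and it keeps the point minor.

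The plan also says losses will be very few. At 0.1% equal loss the y=1 HR is 1.46 against 1.50, and its upper limit stays above 1.5. Crossing 1.5 needs loss of about half the expected PJI incidence or more, which is hard to square with that expectation. This also stands as far as it goes, but the plan gives no rate, and the relevant yardstick is an outcome of only about 1%.

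Third, the plan never promises bounds on the HR. Its labels can be read as describing the patient's outcome, and on that reading the pair does bound each group's incidence. But what is redone is the main analysis, an HR, and for that quantity the worst-case label misleads.

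Fourth, the planned cumulative incidence functions are the usual tool when death precludes the event. That is a partial answer: death is not named as competing there, and the plots do not alter the imputation rule.

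Finally, no direction of bias can be claimed without knowing loss by BMI group. The plan's expectation of no systematic difference may not settle this, because the reason it gives compares missing with observed values rather than obese with non-obese.

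**Conclusion.** The concern holds, at minor severity. Followed as written, the y=1 run codes register-recorded deaths as PJI. The common-value pair does not bracket the HR; that part is algebra and does not depend on the assumed loss rates.

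The size does depend on them. Under the stated assumptions the y=1 run barely moves the HR at 0.1% equal loss and takes 1.50 to 1.34 at 0.5%. The pull toward 1 requires similar loss in both groups. If the obese lose about 1.5 times as many patients, an HR of 1.5 is not diluted, and with a higher ratio it rises. The primary HR and the 1.5 rule are unaffected.

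**What to change.** 1. Take deaths out of the missing-data and imputation paragraph. Suggested text: *Death before a PJI revision (and, for PJI, a first revision for another cause) is a competing event. It is censored in the cause-specific Cox model and counted as a competing event in the cumulative incidence functions.* The follow-up rule already implies the censoring, including at a non-PJI first revision.
2. If extreme-case runs are kept, restrict them to emigration before day 730. Use opposed values in both directions (obese 1 and non-obese 0, then the reverse), and report the results as bounds on the HR, not as a decision rule.
3. In either case, report the numbers of deaths and emigrations in each BMI group, so that readers can judge whether loss is similar.

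The cost is a few sentences and a few lines of code on the same data. The drawback is that opposed bounds are wider. For a true HR of 1.5 they are about 1.37 to 1.60 at 0.1% emigration and 1.00 to 2.01 at 0.5%, so they say little unless emigration is rare. They should not be set directly beside y=1 results that include deaths.

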## Sensitivity analyses

A sensitivity analysis will also be done to report PJI-likely revisions and the microbial profiles in these patients. PJI-likely revisions will be defined as revisions surgeries with at least one of the following: A) One single intraoperatively obtained positive culture obtained from the revision surgery (aspiration fluid OR tissue biopsy) regardless of the microorganism. B) One single positive culture obtained from aspiration of synovial fluid regardless of microorganism. If we do not find a difference between obese and non-obese, we will run a sensitivity analysis where we compare morbidly obese patients ( $BMI \geq 40 \text{ kg/m}^2$ ) with other patients ( $BMI < 40 \text{ kg/m}^2$ ). If the primary analysis showed a difference between obese and non-obese, a sensitivity analysis comparing morbidly obese ( $BMI \geq 40 \text{ kg/m}^2$ ) with non-morbidly obese ( $BMI 30-40 \text{ kg/m}^2$ ) will be done.

**Sensitivity analysis table 1:** Incidence for Periprosthetic joint infection-likely (PJI) revision at 2 years in obese and non-obese patients with the relative risk (RR) and an unadjusted and adjusted analyses of the Hazard Ratios (HR) between the 2 groups

|                           | Obese   | Non-Obese | HR [95% CI*]  |
|---------------------------|---------|-----------|---------------|
| Crude analyses:    |         |           |               |
| N                         | xx      | xx        |               |
| PJI-likely, no. (%)       | xx (xx) | xx (xx)   | xx [xx to xx] |
| Adjusted analyses: |         |           |               |
| N                         | xx      | xx        |               |
| PJI-likely, no. (%)       | xx (xx) | xx (xx)   | xx [xx to xx] |

\*CI: Confidence Interval

**Sensitivity analysis table 2:** Prosthetic joint infection-likely (PJI-likely) within the first 90 days and in 91 days-2 years postoperatively stratified by the type of infection

|   | Obese   | Non-Obese | Absolute Risk difference [95% CI*] |
|---|---------|-----------|------------------------------------|
| N   | xx      | xx        |                                    |
| PJI-likely, 90 days, no. (%)           | xx (xx) | xx (xx)   | xx [xx to xx]                      |
| Staphylococcus aureus, no. (%)                | xx (xx) | xx (xx)   | xx [xx to xx]                      |
| Coagulase-negative staphylococci, no. (%)     | xx (xx) | xx (xx)   | xx [xx to xx]                      |
| Other gram-positive, no. (%)                  | xx (xx) | xx (xx)   | xx [xx to xx]                      |
| Gram-negative, no. (%)                        | xx (xx) | xx (xx)   | xx [xx to xx]                      |
| Anaerobes, no. (%)                            | xx (xx) | xx (xx)   | xx [xx to xx]                      |
| Fungal, no. (%)                               | xx (xx) | xx (xx)   | xx [xx to xx]                      |
| Mycoplasma, no. (%)                           | xx (xx) | xx (xx)   | xx [xx to xx]                      |
| Multibacterial, no. (%)                       | xx (xx) | xx (xx)   | xx [xx to xx]                      |
| PJI-likely, 91 days - 2 years, no. (%) | xx (xx) | xx (xx)   | xx [xx to xx]                      |
| Staphylococcus aureus, no. (%)                | xx (xx) | xx (xx)   | xx [xx to xx]                      |
| Coagulase-negative staphylococci, no. (%)     | xx (xx) | xx (xx)   | xx [xx to xx]                      |
| Other gram-positive, no. (%)                  | xx (xx) | xx (xx)   | xx [xx to xx]                      |
| Gram-negative, no. (%)                        | xx (xx) | xx (xx)   | xx [xx to xx]                      |
| Anaerobes, no. (%)                            | xx (xx) | xx (xx)   | xx [xx to xx]                      |
| Fungal, no. (%)                               | xx (xx) | xx (xx)   | xx [xx to xx]                      |
| Mycoplasma, no. (%)                           | xx (xx) | xx (xx)   | xx [xx to xx]                      |
| Multibacterial, no. (%)                       | xx (xx) | xx (xx)   | xx [xx to xx]                      |

\*The 95% confidence intervals (CI) will not be adjusted for multiplicity and should not be used in place of hypothesis testing.

**Sensitivity analysis table 3:** Incidence for Periprosthetic joint infection (PJI) and all cause revision at 2 years in morbidly obese and non-morbid patients with an unadjusted and adjusted analyses of the Hazard Ratios (HR) between the 2 groups

|                                     | Morbidly-Obese | Non-morbid | HR [95% CI*]  |
|-------------------------------------|----------------|------------|---------------|
| Crude analyses:              |                |            |               |
| N                                   | xx             | xx         |               |
| PJI, no. (%)                        | xx (xx)        | xx (xx)    | xx [xx to xx] |
| Revision due to all causes, no. (%) | xx (xx)        | xx (xx)    | xx [xx to xx] |
| Adjusted analyses:           |                |            |               |
| N                                   | xx             | xx         |               |
| PJI, no. (%)                        | xx (xx)        | xx (xx)    | xx [xx to xx] |
| Revision due to all causes, no. (%) | xx (xx)        | xx (xx)    | xx [xx to xx] |

\*CI: Confidence Interval

**Sensitivity analysis table 4:** Prosthetic joint infection in morbidly-obese within the first 90 days and in 91 days-2 years postoperatively stratified by the type of infection

|  | Morbidly-obese | Non-morbid  | Absolute Risk difference [95% CI*] |
|--|----------------|-------------|------------------------------------|
| N  | xx             | xx          |                                    |
| PJI, 90 days, no. (%)               | xx (xx)        | xx (xx)     | xx [xx to xx]                      |
| Staphylococcus aureus, no. (%)             | xx (xx)        | xx (xx)     | xx [xx to xx]                      |
| Coagulase-negative staphylococci, no. (%)  | xx (xx)        | xx (xx)     | xx [xx to xx]                      |
| Other gram-positive, no. (%)               | xx (xx)        | xx (xx)     | xx [xx to xx]                      |
| Gram-negative, no. (%)                     | xx (xx)        | xx (xx)     | xx [xx to xx]                      |
| Anaerobes, no. (%)                         | xx (xx)        | xx (xx)     | xx [xx to xx]                      |
| Fungal, no. (%)                            | xx (xx)        | xx (xx)     | xx [xx to xx]                      |
| Mycoplasma, no. (%)                        | xx (xx)        | xx (xx)     | xx [xx to xx]                      |
| Multibacterial, no. (%)                    | xx (xx)        | xx (xx)     | xx [xx to xx]                      |
| 
PJI, 91 days - 2 years, no. (%) | 
xx (xx)    | 
xx (xx) | 
xx [xx to xx]                  |
| Staphylococcus aureus, no. (%)             | xx (xx)        | xx (xx)     | xx [xx to xx]                      |
| Coagulase-negative staphylococci, no. (%)  | xx (xx)        | xx (xx)     | xx [xx to xx]                      |
| Other gram-positive, no. (%)               | xx (xx)        | xx (xx)     | xx [xx to xx]                      |
| Gram-negative, no. (%)                     | xx (xx)        | xx (xx)     | xx [xx to xx]                      |
| Anaerobes, no. (%)                         | xx (xx)        | xx (xx)     | xx [xx to xx]                      |
| Fungal, no. (%)                            | xx (xx)        | xx (xx)     | xx [xx to xx]                      |
| Mycoplasma, no. (%)                        | xx (xx)        | xx (xx)     | xx [xx to xx]                      |
| Multibacterial, no. (%)                    | xx (xx)        | xx (xx)     | xx [xx to xx]                      |

\*The 95% confidence intervals (CI) will not be adjusted for multiplicity and should not be used in place of hypothesis testing.

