## Variables

### Outcomes and endpoints

1. The primary outcome is revision due to prosthetic joint infection (PJI) within 2 years following TKA
2. The first secondary outcome is types of microbial profiles detected in the PJs, short term ( $\leq 90$  days) and long-term (91 days to 2 years)
3. Another secondary outcome is revision due to all causes within 2 years following TKA.

For the revision due to PJI, we will stratify the outcome looking into the proportions of the following groups of bacteria within the first 90 days and between 91 and 730 days following TKA:

- A. PJI due to *Staphylococcus aureus*.
- B. PJI due to Coagulase-negative staphylococci.
- C. PJI due to other gram-positive bacteria.
- D. PJI due to gram-negative bacteria.
- E. PJI due to anaerobic bacteria.
- F. PJI due to mycoplasmic infection.
- G. PJI due to polymicrobial infection.
- H. PJI with negative culture.

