## Definitions

**PJI:** our definition of PJI is adapted from The European Bone and Joint Infection Society (EBJIS) criteria as at least one of the following:

- A. DKR-registered revision surgery due to infection.
- B. At least 2 deep-tissue samples of phenotypically indistinguishable bacteria isolated from at least 3 deep-tissue samples
- C. One or more positive intraoperative samples from a closed fluid aspirate AND a biopsy (fluid AND tissue) of phenotypically indistinguishable bacteria isolated.

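### Criterion A makes a register-coded infection revision a primary event without any culture, and no hazard ratio is planned for a stricter, culture-confirmed endpoint

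*Combined protocol and SAP*

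**What the plan says.** All references are to the combined protocol and SAP.

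- **Primary endpoint** (Outcomes and endpoints): "The primary outcome is revision due to prosthetic joint infection (PJI) within 2 years following TKA".
- **What makes a PJI** (Definitions): three criteria, taken "as at least one of the following". Criterion A is "DKR-registered revision surgery due to infection" and asks for no culture. Criterion B is "At least 2 deep-tissue samples of phenotypically indistinguishable bacteria isolated from at least 3 deep-tissue samples". Criterion C needs matching bacteria from both joint fluid and a tissue biopsy. Category H in Outcomes and endpoints, "PJI with negative culture", confirms that events without a positive culture count.
- **Alternative endpoint** (Sensitivity analyses): "A sensitivity analysis will also be done to report PJI-likely revisions and the microbial profiles in these patients". PJI-likely means a revision with one positive culture, from fluid or tissue, of any organism. Sensitivity analysis table 1 gives crude and adjusted hazard ratios for it.
- **Decision rule** (Statistical Methods): absence of a clinically meaningful increase is established "if the upper bound of the 95% confidence interval for the hazard ratio remains below 1.5".
- **Culture-negative events** (Table 3): shown by group as crude proportions and risk differences in each time window, with no hazard ratio.

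**The concern.** The decision rule yields a reassuring conclusion when the hazard ratio is low enough, so dilution towards 1 is not conservative here. A register indication for infection may include revisions that were not infected. If those events are less related to BMI than true PJI is, they pull the estimate down and make the rule easier to meet wrongly.

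The natural check is a more specific endpoint. Criteria B and C already define one that does not depend on the coded indication, and the microbiology database is a listed data source. Yet the only alternative definition asks for less culture evidence than B or C, so one contaminated sample is enough. The remaining sensitivity analyses address other matters: the BMI 40 comparisons change the exposure, and the possible best-case and worst-case imputation concerns missing outcomes.

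The documents also describe no blinded adjudication of the infection indication. If infection is coded more readily in obese patients, the error can go the other way. At stake is whether the main conclusion, in either direction, reflects infection or coding.

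**Working it through.** **1. The plan's own figure.** A 50% increase on a 2-year incidence of about 1% gives a hazard ratio of ln(1 − 0.015) / ln(1 − 0.010) = 1.504, which agrees with the stated 1.5. The documents give no sample size, event count or power to reproduce.

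**2. Dilution.** Let PPV be the share of true PJI among counted events in the non-obese, HR_true the hazard ratio for true PJI, and HR_FP the hazard ratio for false-positive events. Then

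HR_obs = PPV × HR_true + (1 − PPV) × HR_FP.

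With HR_FP = 1 (false positives unrelated to BMI):

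| PPV | HR_obs, true 1.5 | HR_obs, true 1.6 |
|---|---|---|
| 1.0 | 1.50 | 1.60 |
| 0.9 | 1.45 | 1.54 |
| 0.8 | 1.40 | 1.48 |
| 0.7 | 1.35 | 1.42 |

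**3. Effect on the decision rule.** The rule uses the upper 95% limit, so the relevant quantity is

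P(claim) = Φ( (ln 1.5 − ln HR_obs) / SE − 1.96 ), with SE = √(1/e0 + 1/e1),

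where e0 and e1 are the non-obese and obese event counts. Assumptions, not in the documents: 40,000 patients, 45% obese, and the plan's 1% applied to the non-obese. Then e0 = 40,000 × 0.55 × 0.01 = 220 and e1 = 40,000 × 0.45 × 0.01 × HR_obs = 180 × HR_obs.

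For a true hazard ratio of 1.5:

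- PPV 1.0: e1 = 270, SE = 0.091, P = Φ(−1.96) = 2.5%.
- PPV 0.9: e1 = 261, SE = 0.092, P = Φ(0.370 − 1.96) = 5.6%.
- PPV 0.8: e1 = 252, SE = 0.092, P = Φ(0.748 − 1.96) = 11.3%.
- PPV 0.7: e1 = 243, SE = 0.093, P = Φ(1.132 − 1.96) = 20.4%.

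Over 20,000 to 60,000 patients and 35% to 45% obese, the ranges are 4.4–6.6% (PPV 0.9), 7.4–14.8% (0.8) and 11.9–28.3% (0.7). For a true hazard ratio of 1.6, in the 40,000-patient case, the chance goes from 0.4% at PPV 1.0 to 1.2%, 3.5% and 8.6%. These are approximations for an unweighted model.

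**4. Direction.** The bias is nil when HR_FP equals HR_true and changes sign there. At PPV 0.8 and a true hazard ratio of 1.5:

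- HR_FP = 1: 0.8 × 1.5 + 0.2 × 1 = 1.40.
- HR_FP = 1.3: 0.8 × 1.5 + 0.2 × 1.3 = 1.46.
- HR_FP = 2: 0.8 × 1.5 + 0.2 × 2 = 1.60.

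**5. The planned analyses against the gap.** PJI-likely asks for less than B or C. Against A the comparison is mixed: read literally it drops coded revisions with no positive culture (sensitivity analysis table 2 has no culture-negative row), but it lets in revisions with one positive sample. The text does not say whether PJI-likely replaces the primary events or is added to them. Table 3 does not isolate A-only events either: a coded infection with one positive culture can meet A alone and still sit in an organism row.

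**The case against.** A reader might infer that the plan has no check on coding, that PJI-likely can only push the result further towards no increase, and that the primary hazard ratio is certainly biased towards 1. The documents support none of these.

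- Table 3 shows culture-negative PJI by group, where an excess of culture-negative coding in obese patients could become visible, though only in crude proportions.
- If PJI-likely replaces the primary events, it removes coded revisions without a positive culture, and its net direction is unknown.
- The sign of the bias depends on HR_FP, which the documents do not give.

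Low specificity of criterion A is itself an assumption. The plan cites a validity assessment of PJI capture in this register, but the documents report no specificity or predictive value from it.

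The dilution must also be large before the expected estimate itself meets the rule. In the 40,000-patient case with SE about 0.095, the observed hazard ratio must be about 1.5 × exp(−1.96 × 0.095) = 1.25 or lower. With HR_FP = 1 that takes a false-positive share of 1 − 0.25/0.5 = 50% at a true 1.5, or 1 − 0.25/0.6 = 58% at a true 1.6. This stands as a limit on the size of the problem. It does not remove the rise in the false-claim rate at smaller shares.

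Finally, a B-or-C endpoint has its own weakness. B needs at least three tissue samples and C needs both fluid and tissue, and nothing says that sampling is independent of BMI or of suspected infection. It also leaves out true culture-negative PJI, which the plan counts on purpose. This is a good reason to keep the endpoint supporting and not to make the main claim depend on it.

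**Conclusion.** The gap is real and limited. Criterion A suffices without a culture, the only alternative definition asks for less than B or C, and no culture-confirmed hazard ratio is planned beside a rule that non-specific events can favour. If false positives are unrelated to BMI, the chance of a wrong claim at a true hazard ratio of 1.5 rises from 2.5% to about 6% at PPV 0.9 and about 11% at PPV 0.8. This rests on the assumed cohort size, obese share, incidence and PPV. If false positives are more strongly related to BMI than true PJI is, the primary hazard ratio is too high instead. The documents do not settle which applies, and a strict analysis is informative either way. It is a cheap improvement to the sensitivity analyses and not a reason to change the primary endpoint.

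**What to change.** Keep the primary endpoint and the 1.5 rule. Then:

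1. In Sensitivity analyses and sensitivity analysis table 1, add crude and inverse-probability-weighted Cox hazard ratios for first revision meeting criterion B or C, whatever indication the register gives.
2. Report, by group, how many primary events meet criterion A only.
3. State whether PJI-likely replaces the primary events or is added to them.
4. Show the B-or-C interval beside the primary one when the below-1.5 conclusion is discussed, without making it a formal condition.

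The cost is one more set of models on data already linked and a few table rows. The downsides are fewer events, a wider interval, the loss of true culture-negative PJI, and dependence on how often samples were taken. These should be stated with the result.
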